BMI	Body Mass Index
CSR	Clinical Study Report
EDC	Electronic Data Capture
EOS	End of Study
EOT	End of Treatment
ERT	Evaluation of Response to Treatment
IRB	Institutional Review Board
ITT	Intent to Treat
LOCF	Last Observation Carried Forward
LSR	Local Skin Reactions
MedDRA	Medical Dictionary for Regulatory Activities
mm	Millimeter
PERIT	Patient Evaluation of Response to Investigational Treatment
RTF	Rich Text Format
SAP	Statistical Analysis Plan
SERT	Safety Evaluation of Response Treatment
TEAE	Treatment Emergent Adverse Event
TFL	Tables, Figures, Listings
WHO	World Health Organization

1. Introduction

Verrica Pharmaceuticals, Inc. is conducting a study under the protocol name “A Phase 2, Open-Label Study to Evaluate the Efficacy, Safety and Tolerability of VP-102 in Subjects with Common Warts (Verruca Vulgaris)”. The study background, design and subject assessments for the study are described in the study specific protocol.

The statistical methods to be implemented during the analyses of data collected within the scope of this study (VP-102-105) will be outlined in this document. The purpose of this plan is to provide specific guidelines from which the statistical analysis will proceed. Any deviations from this plan will be documented in the clinical study report.

This Statistical Analysis Plan (SAP) specifies the planned analyses and reporting of data from Cohort 2 of this study only, as described in Version 3 dated 01 November 2018 of the study protocol. Analyses of Cohort 1 or any future cohorts or study parts will be addressed in an updated or separate SAP.

2. Study Rationale and Objectives

2.1. Study Rationale

The protocol states: “For many dermatologists, 0.7% w/v cantharidin has been the treatment of choice for warts for decades. However, cantharidin remains an unapproved drug, and there is no reliable or controlled source on the market. This study will evaluate VP-102, a controlled, highly-pure, standardized form of topical cantharidin manufactured under good manufacturing practices to address the problems associated with currently available compounded cantharidin products and the needs of subjects and medical professionals.”

2.2. Study Objectives

2.2.1. Primary Objectives

The primary objectives for Cohort 2 are (1) to evaluate the efficacy of dermal application of VP-102 when applied once every 21 days for up to 4 applications to common warts on subjects 12 years and older by assessing the proportion of subjects achieving complete clearance of all treatable warts at the EOT Visit (Day 84) and (2) to assess the safety and tolerability of VP-102 applied to common warts by assessing adverse events including expected local skin reactions, physical examinations, and concomitant medications.

2.2.2. Secondary Objectives

The secondary objectives of this study are:

- to evaluate the efficacy of VP-102 by assessing the change from baseline in the

- number of treatable warts (baseline and new) at the EOT visit (Day 84).
- to evaluate the efficacy of VP-102 by assessing the change from baseline in the percent of clearance of treatable warts (baseline and new) at the EOT visit (Day 84).
- to evaluate the efficacy of VP-102 by assessing the proportion of subjects exhibiting complete clearance of all treatable warts (baseline and new) at Treatment Visit 2, Treatment Visit 3, Treatment Visit 4.

2.2.3. Exploratory Objectives

Exploratory objective is:

- to evaluate the efficacy of VP-102 by assessing the proportion of subjects exhibiting complete clearance of all treatable warts (baseline and new) at follow-up visits on Days 105, 126 and 147.
- to assess endpoints other than clearance that may be indicative of treatment efficacy.

3. Study Design

This is a Phase 2, open label, multi-center study [Study number VP-102-105; referred to as COVE-1 (Cantharidin and Occlusion in Verruca Epithelium)] that will be conducted in the United States to determine the safety, efficacy and tolerability of VP-102 treatment in subjects with common warts.

This study has two Cohorts. The second Cohort (Cohort 2) utilizes a treatment interval of 21 days between treatments. Paring of lesions is allowed in Cohort 2 only.

Approximately 35 subjects (12 years and older) will be enrolled in Cohort 2. Up to 4 sites will participate in the study.

All subjects will receive the Study drug VP-102 (0.7% w/v cantharidin topical film-forming solution). Duration of warts prior to Treatment Visit 1 must be at least 4 weeks.

Study drug (VP-102) will be supplied in single-use applicators, with one applicator having sufficient volume to treat 1-6 common warts. No more than 1 applicator will be permitted per subject per treatment. VP-102 will be applied and left on the warts, under occlusive tape, for 24 hours before the subject/guardian removes the occlusive tape and washes the warts with soap and warm water. Occlusive tape and Study drug may be removed prior to the 24-hour time point in the event significant blistering, significant pain or treatment-emergent adverse events (TEAEs) are experienced.

Treatment will be applied up to four times during a 75-day treatment period for Cohort 2. The treatment interval in Cohort 2 is 21 days.

It can sometimes be challenging to determine if a wart is completely clear after treatment due to ongoing local skin reactions. At any visit where the investigator is unable to evaluate or treat some warts due to ongoing local skin reactions, an “Unscheduled” Visit should be documented. The timing of the next visit will be determined by the resolution of the local skin reaction. A Treatment Visit should be documented at every visit where Study drug is applied. Treatment should only take place at a visit when all warts are evaluable (i.e., not obscured by an ongoing LSR) and all warts that are not completely clear, should undergo treatment with Study drug. No partial treatment of warts is permitted.

For Cohort 2, study drug is to be applied to the wart site on any Treatment Visit where a new clinical assessment of complete clearance is made for that wart (e.g., if a patient returns for Treatment Visit 2 and is clinically assessed to have no visible evidence of a remaining wart, then Study drug is still to be applied to this wart site at Treatment Visit 2. However, if the patient remains completely clear at that wart site when returning for a subsequent visit such as Treatment Visit 3, then no Study drug would be applied at Treatment Visit 3.) Should it become clear that the subject will be unable to complete the EOT visit within the allowed window of Day 84 (+/- 8) days, the subject should be brought in for their EOT visit as soon as they are able. This will be documented as a protocol deviation.

In instances where the clinician can adequately assess the treatment sites but is uncertain if a residual wart is remaining, treatment should be applied, and the subject should return for evaluation per protocol. Treatment visits and assessments are to take place in order (e.g., Treatment 1, Treatment 2, Treatment 3 and Treatment 4). Subjects that receive fewer than 4 treatments within the 75-day (Cohort 2) treatment period, due to the duration of post-treatment local skin reactions, will not be considered a protocol deviation. No treatment should be administered after the 75-day treatment period in Cohort 2 without Sponsor’s approval.

Subjects in Cohort 2 will undergo wart paring with a sharp surgical instrument (e.g., scalpel or flexible medical blade) to remove any adherent thick scale from a wart prior to application of Study drug. Wart paring is to be performed at any Treatment Visit when adherent thick scale is present, and the investigator considers that it can be safely performed. Paring should be conducted by a trained practitioner and in compliance with any local regulations and should be discontinued when it results in punctate bleeding or significant pain. Not all warts may require paring and, if adherent scale is not present, then Study drug can be applied without paring. Subjects should be re-treated only after 17 days (i.e., 21 +/- 4 days) have elapsed in Cohort 2, but only after any LSR has resolved

sufficiently to allow evaluation of the treatment site. Treatment should be administered within 4 days of becoming eligible due to resolution of LSRs.

For Cohort 2, subjects are to attend all visits regardless of whether they have achieved complete clearance prior to and at the Day 84, (+/- 8 days) EOT assessment.

Subjects in Cohort 2 will participate in an in-person EOT evaluation at Day 84 (+/- 8). A provider EOT Questionnaire will be completed at the EOT Visit. Cohort 2 subjects will continue in the study for 3 additional follow-up assessments at Day 105, Day 126 and Day 147. The follow-up visit window is +/- 4 days.

To assist the research team in the ERT phone calls, education materials in the form of a local skin reaction guide with specific photos identifying the various skin reactions and examples of intensity will be reviewed at the clinic with the subject/guardian by the research team. Should a subject report experiencing excessive blistering, ulceration, edema, pain or another adverse event needing physician assessment during the ERT call, they will be scheduled for an "Unscheduled" study visit and safety evaluation as soon as possible.

Subjects 18 and older must provide consent as required by the IRB before any study procedures are conducted. Parents or guardians must provide informed consent, and pediatric subjects older than 10 years must provide assent as required by the IRB before any study procedures are conducted. Subjects must meet all study eligibility criteria through a complete review of pertinent medical history, a dermatologic exam/wart count and physical examination.

4. Determination of Sample Size

The study will enroll subjects with common warts for the main efficacy purpose of obtaining information on clearance rates of the warts in response to VP-102 therapy. Subjects will continue to be enrolled into Cohort 2 of the study until approximately 35 subjects are enrolled. Due to the exploratory nature of the study, no formal sample size estimates will be carried out for powering purposes.

5. Statistical Methods

The statistical analyses described in this document are specific to Cohort 2 of this study and will be reported using summary tables, figures and listings (TFLs). Numbering for TFLs will be based on the recommended numbering convention provided by the International Conference on Harmonization. Continuous variables will be summarized with means, standard deviations, medians, minimums and maximums. Categorical

variables will be summarized by counts and percent of subjects in corresponding categories. Where appropriate, 95% confidence intervals may be included. Missing values are not considered for percent calculations, unless stated otherwise. In those cases, footnotes will specify the percent basis.

Individual subject data obtained via the electronic data capture (EDC) system and from external vendors will be presented in listings.

The analyses described in this plan are considered *a priori*, in that they have been defined prior to database lock. Any analysis added after the database lock will be considered *post hoc* and exploratory. *Post hoc* analyses will be labeled as such on the output and identified in the CSR. All analyses and tabulations will be performed using SAS® version 9.3 or higher. Tables and listings will be presented in .rtf or .pdf format. Upon completion, all SAS programs will be validated by an independent programmer. The validation process will be used to confirm that statistically valid methods have been implemented and that all data manipulations and calculations are accurate. Checks will be made to ensure accuracy, consistency with this plan, consistency within tables and consistency between tables and corresponding data listings.

6. Analysis Populations

Intent to Treat (ITT) Population:

The Intent-to-Treat population (ITT) will include all subjects enrolled in the study.

Per Protocol Population:

Subjects who receive all 4 planned treatments of VP-102 (e.g., up to four treatments within the 75-day treatment window or cleared of all treatable warts prior to Day 75), are assessed for clearance at the EOT visit, and have no major protocol violations, will be included in the Per Protocol population. Major protocol deviations will be evaluated prior to excluding subjects from the per Protocol population. Major deviations will be determined via a clinical review of all deviations; criteria for major deviations include the following:

- Failure to obtain informed consent;
- Informed consent was incorrect or incomplete;
- Non-compliance with inclusion/exclusion criteria;

- IP administration/dosing errors;
- Non-compliance with study protocol procedures;
- Unreported serious adverse events.

In addition, the following pre-determined reasons will exclude subjects from being included in the Per Protocol population:

- Subjects who do not come in for required treatment visits
- Subjects who do not return for the EOT study visit
- Subjects who refuse to have all of their treatable warts treated or investigators who refuse to treat all treatable warts
- Early removal of the study drug not associated with pain, blistering or other medically appropriate reason for early removal. Early removal will be determined by the defined study window of 24 hrs +/- 8 hrs.
- Subjects who begin alternative treatments for their warts after starting the study
- Subjects enrolled who did not meet the inclusion/exclusion criteria

Safety Population:

The Safety population will include subjects who receive at least one treatment of VP-102.

7. Study Population

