9.2.2 Populations of Interest

The intent-to-treat (ITT) population will include all subjects enrolled in the study.

Subjects who receive all planned treatments of VP-102 (e.g., up to four treatments within the 63 day treatment window, or cleared of all treatable warts prior to Day 63 in Cohort 1; and in Cohort 2 complete up to four treatments within the Day 75 treatment window or clear prior to Day 75) are assessed for clearance at the EOS visit and have none of the following major protocol violations will be included in the Per Protocol population. The following pre-determined reasons will exclude subjects from being included in the Per Protocol population:

- Subjects who do not come in for required Treatment Visits.
- Subjects who do not return for the EOS study visit.
- Subjects who refuse to have all of their treatable warts treated or investigators who refuse to treat all treatable warts.
- Early removal of the study drug not associated with pain, blistering or other medically appropriate reason for early removal.
- Subjects who begin alternative treatments for their warts after starting the study.
- Subjects enrolled who did not meet the inclusion/exclusion criteria.

The safety population will include subjects who receive at least one treatment of VP-102.

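### The SAP's Per Protocol rule contradicts itself on whether four applications are required; read literally, it keeps or drops reaction-delayed subjects according to whether they cleared

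*SAP*

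**What the plan says.** SAP Section 6 begins the Per Protocol definition with "Subjects who receive all 4 planned treatments of VP-102" and qualifies it in a bracket: "e.g., up to four treatments within the 75-day treatment window or cleared of all treatable warts prior to Day 75". The subject must also be assessed for clearance at EOT and have no major protocol violation. A list of further exclusions follows, including "Subjects who do not come in for required treatment visits"; that one applies whatever the outcome.

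Protocol 9.2.2 has no 4. It begins "Subjects who receive all planned treatments of VP-102 (e.g., up to four treatments within the 63 day treatment window" and for Cohort 2 continues "in Cohort 2 complete up to four treatments within the Day 75 treatment window or clear prior to Day 75". The Statistical methods part of the Synopsis has the same wording.

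On the subject who falls short because of skin reactions, SAP Section 3 speaks of "Subjects that receive fewer than 4 treatments within the 75-day (Cohort 2) treatment period, due to the duration of post-treatment local skin reactions" and says this is not a protocol deviation. Protocol 4.1 says the same.

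ITT is the primary analysis set (SAP Section 8, Protocol 9.2.3), and Protocol 9.2.3 calls the Per Protocol analysis secondary.

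**The concern.** The opening words and the bracket give two different populations. They differ for one group: subjects who attended their visits, received fewer than four applications because skin reactions delayed treatment, and had not cleared before Day 75. The opening words drop them and the bracket keeps them. Comparable subjects who did clear are kept either way, through "or cleared of all treatable warts prior to Day 75".

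Under the literal reading, then, clearance decides who stays among subjects with the same shortfall. Clearance before Day 75 is not the primary endpoint, which is clearance at EOT (Day 84), but the two are closely related. If the dropped subjects clear less often at EOT than the rest, the Per Protocol rate rises with no change in efficacy.

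The Protocol Synopsis says the clearance rates should support assumptions for later placebo-controlled trials, so a rate that moves with the reading of one sentence matters even in a descriptive study.

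**Working it through.** The plan states no expected clearance rate, Per Protocol size or rate of treatment delay, so there is no figure to reproduce. The check has two parts.

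**1. Can a compliant subject fall short of four applications by Day 75?**

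Inputs: interval 21 ± 4 days and last treatment Day 75 (Protocol Table 2, notes b and c). All warts must be evaluable before any is treated (SAP Section 3), so one obscured wart postpones the whole session.

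- Nominal fourth application: Day 1 + 3 × 21 = Day 64, which leaves 75 − 64 = 11 days.
- Longest permitted intervals: Day 1 + 3 × 25 = Day 76, already past Day 75.
- Assume each interval is a whole number of days, equally likely from 17 to 25, plus one 10-day delay. The fourth application passes Day 75 when the three intervals sum to at least 65 days: 274 of 9³ = 729 combinations, or 37.6%. This is conditional on such a delay; it is not an estimate of how many subjects are affected.

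**2. How far could the rate move?**

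Let N = 35 (the approximate Cohort 2 enrolment target), x = subjects clear at EOT, u = reaction-delayed subjects uncleared before Day 75 but otherwise eligible, and c = those of the u who are clear at EOT. All other Per Protocol exclusions are set to zero. x, u and c are assumptions.

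- Bracket reading: rate = x/N.
- Literal reading: rate = (x − c)/(N − u).

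The literal rate is the higher one when N(x − c) > x(N − u), that is, when c/u < x/N: the dropped subjects clear at EOT less often than the cohort as a whole.

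With x = 15, the bracket reading gives 15/35 = 42.9% for every u. The literal reading gives:

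| u | none clear at EOT | half clear | all clear |
|---|---|---|---|
| 2 | 15/33 = 45.5% | 14/33 = 42.4% | 13/33 = 39.4% |
| 4 | 15/31 = 48.4% | 13/31 = 41.9% | 11/31 = 35.5% |
| 6 | 15/29 = 51.7% | 12/29 = 41.4% | 9/29 = 31.0% |
| 8 | 15/27 = 55.6% | 11/27 = 40.7% | 7/27 = 25.9% |

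For other starting rates, with u from 2 to 8 and c = 0:

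- 10/35 (28.6%) becomes 30.3% to 37.0%.
- 18/35 (51.4%) becomes 54.5% to 66.7%.
- 25/35 (71.4%) becomes 75.8% to 92.6%.

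**The case against.** The strongest reply is that the literal reading was never intended. The bracket explains the opening words, the protocol has no 4, a shortfall from skin reactions is expressly not a deviation, and it is not among the listed exclusions. On that reading the subjects stay in and the distortion is zero. This stands as a reason not to treat exclusion as settled, but it does not remove the conflict. If any number of applications up to four is enough, the 4 and the clearance alternative do no work. SAP Section 8 also describes treatment as planned every 21 days while warts persist, up to four times, so even the protocol's wording could be taken to mean four for an uncleared subject. A programmer has to choose.

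A reader might infer that the rule removes only failures, so that the Per Protocol rate must be too high. The documents do not support that. The clause concerns clearance before Day 75 and the endpoint is EOT. A dropped subject may be clear at EOT, and a kept subject may recur and then counts as not cleared (SAP Section 8). The table shows the direction can reverse.

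A reader might also infer that the clearance clause should go. That does not follow. In Cohort 2 a site that remains clear at the next treatment visit receives no further drug (SAP Section 3), so an early clearer can have had every planned application with fewer than four.

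Finally, the reach is limited. Missed visits exclude cleared and uncleared subjects alike, no formal comparison is planned (SAP 8.6), and neither document gives the Per Protocol analysis the task of confirming ITT. All of this stands, and it bounds the consequence.

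**Conclusion.** The contradiction, within the SAP sentence and against the protocol, is on the page and needs no assumption. That it makes membership depend on clearance holds under the literal reading only. That it raises the Per Protocol rate is probable, because subjects still uncleared when treatment ends are likely to clear at EOT less often than the rest, but it is not certain.

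The size rests on assumed counts: from 43%, a rise of about 3 to 13 points if 2 to 8 subjects are dropped and none is clear at EOT, and less or negative otherwise. For scale, the exact 95% confidence interval around 18/35 runs from 34.0% to 68.6%, so shifts of this size lie within the sampling uncertainty of the cohort. The primary ITT result is untouched. This is a point that should be corrected, in a secondary descriptive analysis.

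**What to change.** Before database lock, make two changes to SAP Section 6.

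1. Delete the 4 from the opening words, so that they match the protocol's requirement of all planned treatments, up to four.
2. State that a subject with fewer than four applications solely because of skin-reaction delay within the 75-day period stays in the Per Protocol population whether or not the warts cleared, provided required visits were attended, clearance was assessed at EOT and there was no major deviation. Deletion alone would leave room to read the plan as four for anyone uncleared.

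Say also that a visit attended but recorded as Unscheduled because of a skin reaction counts as attended. SAP Section 8 names a treatment visit only when drug was applied or all warts were marked cleared, so the missed-visit exclusion could otherwise bring the same asymmetry back.

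The clause for early clearers may stay. The cost is SAP wording; the Per Protocol rate may come out slightly lower than under the literal reading.

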7.1. Subject Disposition

Information regarding subject disposition will be summarized for all subjects. Summaries will include: number of subjects in each analysis population, number of subjects who completed the treatment phase of the study, number of subjects assessed for clearance at the End of Treatment Visit (EOT), number of subjects completing the study, and number of subjects who discontinue the study early. Subjects will be considered to have completed the treatment phase of the study if they had a Day 84 (EOT) visit. In order for a subject to be considered to have completed the study, they must have completed their Day 147 visit. For those who discontinue early, the primary reason for early termination will be summarized.

7.2. Protocol Deviations

Protocol deviations will be collected throughout the duration of the study. Protocol deviations will be assigned a sponsor-defined category type. Each deviation will be defined as major or minor. A tabular summary of all major deviations will be generated.

In addition, a by-subject listing of all protocol deviations (major and minor) will be produced.

